Of the above feasibility measures, selected outcomes were used as key markers to assess if further investigations were warranted for the future. The following criteria for evaluating feasibility are below:

1. No adverse events related to the intervention treatment.
2. Sample size of 30 participants per trial.
3. Consent rate no less than 80%.
4. Retention rate no less than 80%.
5. Attendance rates no less than 80%.

If all five criteria were met, then further investigations can continue without modification.

If three to four criteria were met, then further investigations can continue with modifications. If two or less criteria were met, the study is assessed as not feasible.

Secondary outcomes

All secondary outcome assessments were taken pre and post-intervention. Testing protocols required participants to avoid strenuous physical activity 48 hours prior to testing days.

Assessments took a single session to complete and all participants were tested within similar time periods.

Bioelectric Impedance Analyzer. In a separate private room, one participant at a time weighed themselves on a certified scale. Participants used the handheld Omron model HBF-306 to enter their weight, age, sex and activity level. Resulting BMI and body fat percentage data was recorded. Omron HBF-306 has been shown to be a reliable tool to track body composition over time [49].

Isometric lower body pull. Using the Baseline 12-0400 Back-Leg-Chest dynamometer participants stood up-right and feet hip width apart on the dynamometer platform with the chain adjusted so the handle was at the intra-articular space of the knee joint. Participants were instructed to grip the handle evenly at the center then produce a maximal 5 sec pull keeping the back from bending and arms straight. Participants were allowed to rest 30 sec between attempts. Participants had one practice attempt for familiarization purposes and then the best score of the three following attempts were recorded. Prior research has established reasonable test-retest reproducibility of the Baseline 12-0400 Back-Leg-Chest dynamometer in adolescent populations [50].

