90° push-up. Participants were paired; participant 1 performed the test while participant 2 recorded the number of push-ups. Participants performed the assessment in accordance with the Cooper Institute's procedures [45]. Participant 1 assumed a prone plank position with hands slightly outside of shoulders, fingers stretched out and legs straight with a slight gap. While performing push-ups, the participants' back maintained a straight line from head to ankles. Participants started by lowering their body until the upper arms became parallel to the ground. The participant then extended their arms straight pushing their body up. This movement was

performed every three seconds by metronome and repeated until failure. Participants were allowed one form correction and two form corrections resulted in test termination. Form corrections included participants stopping to rest, a failure to maintain a straight back, achieving proper depth or fully extending the arms. Prior research notes the acceptable reliability of the push-up assessment in males and females [51].

Modified Pull-up. Participants performed the modified pull-up test in accordance with Cooper Institute's procedure [45]. Participants placed a barbell in a squat rack so that the barbell was one to two inches away from participant's reach while supine on the ground. A band was then placed seven to eight inches below the barbell. Participants started the assessment by overhand gripping the barbell and creating a straight line from head to heels so that only the heels were in ground contact. Participants then pulled their body toward the barbell until the chin was above the band. This movement was performed every three seconds by metronome and repeated until failure. Participants were allowed one form of correction and two form corrections would result in test termination. Form corrections included participants stopping to rest, failure to maintain a straight line, achieve proper depth and fully extending the arms.

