PACER. To assess cardiovascular fitness, the Progressive Aerobic Cardiovascular Endurance Run (PACER) assessment was used. Prior to the start of assessment, the primary investigator measured and marked a designated 20-meter distance in the gymnasium for testing. Participants were briefed on the assessment guidelines and participated in one practice opportunity prior to the official assessment. Once familiarized, participants ran the 20-meter distance in accordance to PACER cadences from the Cooper Institute for as long as possible. The test was terminated when the participant voluntarily stopped due to fatigue or when two laps were missed. The primary researcher recorded total number of successful levels. Once

completed, the primary researcher computed predicted peak VO₂ by using VO₂peak = 0.353(Laps) – 1.121(Age) + 45.619. This equation has been shown to have moderately strong linear relationships compared to measured VO₂ peak of adolescents [52].

Quantitative data analysis

Non-parametric analyses of primary and secondary outcomes were used due to the small sample size. Wilcoxon signed rank tests were used to test significance of pre and post-intervention data within treatment groups. Reports of Wilcoxon signed rank included medians, inner quartile ranges, z scores and p-values. Two sample Wilcoxon rank sum (Mann-Whitney) tests were used to test significance between treatment group differences. Reports of Wilcoxon rank-sum (Mann-Whitney) tests included medians, inner quartile ranges, U statistic and p-values. Due to an underpowered sample, effect sizes were calculated for all secondary outcome statistical tests. Given the exploratory nature of this study and the small sample, effect sizes may be more useful in guiding future research. Effect sizes were interpreted as small if $r = 0.2 - 0.5$, medium if $r = 0.5 - 0.8$ medium and large if $r > 0.8$. Statistical package STATA (version; BE 18.0, StataCorp, College Station, Texas, USA) was used and Alpha level was set at $P < 0.05$.

Qualitative assumptions

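### One set of small/medium/large labels is applied to an undefined r for both the signed-rank and the rank-sum tests, so at these arm sizes the labels depend on the formula and are not comparable between tests

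*Combined protocol and SAP*

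**What the plan says.** The Quantitative data analysis section uses Wilcoxon signed-rank tests for pre-to-post change within each arm and rank-sum (Mann-Whitney) tests between arms. It states that "effect sizes were calculated for all secondary outcome statistical tests", so both kinds of test carry an effect size. A single grading applies: effect sizes are "interpreted as small if $r = 0.2 - 0.5$, medium if $r = 0.5 - 0.8$ medium and large if $r > 0.8".

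Neither this section nor any other gives a formula for r, says what N is, or cites a source for the cut-offs. The reporting lists differ by test. For the paired test, "Reports of Wilcoxon signed rank included medians, inner quartile ranges, z scores and p-values"; for the between-group test, "Reports of Wilcoxon rank-sum (Mann-Whitney) tests included medians, inner quartile ranges, U statistic and p-values". So z is listed for one and U for the other.

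The same section gives these effect sizes weight: "Given the exploratory nature of this study and the small sample, effect sizes may be more useful in guiding future research".

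**The concern.** Several coefficients for rank tests are called r. For the signed-rank test, z may be divided by the square root of the number of pairs or of the number of observations. For the rank-sum test, r may be z/√N or the rank-biserial correlation obtained from U. With arms of three or four these choices move results across the cut-offs.

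Even when the same z-based form is used for both tests, a *large* within-arm label and a *large* between-group label need very different data. The plan presents effect sizes as the more useful guide for later work. A reader who carries the labels forward could therefore be comparing metrics and not effects.

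**Working it through.** **Inputs.** Seven participants, four male and three female (Participants); two arms, randomised with stratification by sex (Experimental design); cut-offs as quoted. The plan gives no r value to reproduce.

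**Assumptions, because the documents are silent.** Arms of 3 and 4, with 2 and 5 as sensitivity; before- and after-school cohorts pooled; all seven analysed, although the Fidelity rule can remove post-intervention data; no ties, no zero changes, no continuity correction. Chance means no effect, with all sign patterns or arm arrangements equally likely.

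**1. Within arms.** z = (W − n(n+1)/4) / √(n(n+1)(2n+1)/24). If everyone changes in the same direction:

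- n = 3: z = (6 − 3)/√3.5 = 1.604. z/√3 = 0.926 (*large*); z/√6 = 0.655 (*medium*).
- n = 4: z = (10 − 5)/√7.5 = 1.826. z/√4 = 0.913 (*large*); z/√8 = 0.645 (*medium*).

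The next values of z/√n are 0.617 (n = 3) and 0.730 (n = 4), so *large* means exactly that all change in one direction. By chance this is 2/8 = 25% and 2/16 = 12.5%.

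Under z/√(2n), *large* is impossible at any n. Write z = Σ(sign × rank)/√Σ(rank²). This is at most √n, so z/√(2n) is at most 1/√2 = 0.707. At the planned 15 per arm the maximum is 0.622.

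Switching between n and 2n changes the label in 4 of 8 sign patterns at n = 3 and 4 of 16 at n = 4.

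**2. Between groups.** z = (U − n₁n₂/2) / √(n₁n₂(N+1)/12); rank-biserial = 2U/(n₁n₂) − 1.

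| Arms | U | z | z/√N | Rank-biserial |
|---|---|---|---|---|
| 3 v 4 | 12 of 12 | 6/√8 = 2.121 | 0.802 *large* | 1.000 *large* |
| 3 v 4 | 11 of 12 | 5/√8 = 1.768 | 0.668 *medium* | 0.833 *large* |
| 2 v 5 | 10 of 10 | 5/√6.667 = 1.936 | 0.732 *medium* | 1.000 *large* |

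At 3 v 4, *large* under z/√N needs complete separation: 2 of 35 arrangements, 5.7%. Under rank-biserial it is 4 of 35, 11.4%. At 2 v 5, even perfect separation is only *medium* under z/√N.

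**3. The two tests compared, per test, at 3 v 4.** Within arms, z/√n: (25% + 12.5%)/2 = 18.75%. Between groups, z/√N: 5.7%. The ratio is about 3.3.

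**4. Ties and zeros.** Push-ups are a count ("participant 1 performed the test while participant 2 recorded the number of push-ups"), as are pull-ups, and for PACER "The primary researcher recorded total number of successful levels", so ties are plausible. Over all tied and untied orderings of seven values at 3 v 4, separated patterns give z/√N of 0.802 to 0.926 and all others at most 0.778, so the separation rule survives ties. At 2 v 5 it does not stay out of reach: four tied values in the larger arm bring complete separation to 0.808. Within arms, if a zero change is kept in the ranking and everyone else changes in one direction, z/√n is 0.801 (n = 3) or 0.836 (n = 4). With two zeros it falls to 0.577 or 0.700.

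**The case against.** The strongest reply is that little hangs on this. The Sample size section says the study was not meant to report powered differences, the analysis section calls it exploratory, and none of the five progression criteria uses r. That stands and limits the size of the point.

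A second reply is that a reader given z, U and the arm sizes can recompute any version of r, apart from ties when moving from U to z. That also stands: the ambiguity is in the label, not in the underlying statistic. But the labels are how the plan says effect sizes were interpreted.

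Third, the difference in ceilings exists only under z/√N. Under rank-biserial both tests reach 1.0. This is correct, but the coefficients still measure different things (consistency of change within an arm, separation between arms), which is a reason not to share labels.

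Three stronger readings are tempting and not supported:

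- A reader might infer that the cut-offs were borrowed from a standardised mean difference. No source is cited, so their origin is unknown.
- Over six outcomes, the expected chance *large* labels are 6 × (0.25 + 0.125) = 2.25 within arms and 6 × 2/35 = 0.34 between groups, which might be read as a 6.6-fold contrast. It compares 12 tests with 6; the per-test figures are the fair ones.
- A reader might infer that numerical r values were withheld or that the labels misled. The document contains no outcome results, so neither can be said.

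**Conclusion.** The point holds for the interpretation of exploratory secondary outcomes. One label rule on an undefined r gives labels that depend on an unstated formula and N, and under the z-based forms the same word is reached far more easily within arms than between them: 18.75% against 5.7% per test by chance at 3 v 4.

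The bound of 0.707 for z/√(2n) needs no assumption about arm size. The other figures rest on the assumed split, pooled cohorts, seven analysed, and no ties or zero changes. At 2 v 5 without ties, *large* is unreachable between groups under z/√N.

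A reader might go further and conclude that the feasibility decision is compromised. The documents do not support that, because the progression criteria concern adverse events, sample size, consent, retention and attendance.

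**What to change.** Drop the small/medium/large labels. For each secondary outcome report the Hodges-Lehmann estimate with its exact interval at the attainable confidence level. Between groups this is at most 1 − 2/35 = 94.3% at 3 v 4 or 1 − 2/21 = 90.5% at 2 v 5. Within arms of 3 or 4 it is 1 − 2/8 = 75% or 1 − 2/16 = 87.5%. Beside it give a rank-biserial correlation defined separately for each test, with its N and the handling of ties and zero changes stated.

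If labels are kept, the minimum is to give the formula and N for each test, assign 0.5 to one class only, and state that labels are not comparable between within-group and between-group tests. Lowering the cut-offs would not help: with *large* set at 0.5, chance labels at 3 v 4 under the z-based forms (√n within arms, √N between groups) would rise to 8/35 = 22.9% between groups and to 4/8 = 50% or 6/16 = 37.5% within arms.

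The text describes a completed study, so the change should be declared as post hoc. It needs no new data. The cost is that wide intervals at low confidence become visible. Showing individual changes is optional and subject to confidentiality in arms this small.
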